7. STUDY OBJECTIVES AND ENDPOINTS

7.1 Primary Objective

- The primary objective is to evaluate the safety and tolerability of the GBS-NN/NN2 vaccine for 12 weeks (up to Day 85) after the first dose of vaccine.

7.2 Secondary Objectives

- To evaluate IgG antibody responses induced by the two vaccine doses of GBS-NN/NN2 up to Day 85 in healthy female subjects.
- To assess whether pre-existing antibody levels affect the vaccine-induced antibody response.

7.3

pregnancy.

8.3 Study Duration

Study start is defined as check-in to the study unit on Day 1. Each individual subject will be involved in the study for approximately 12 weeks (excluding the 28 day screening period and the 6 month safety follow up).

9. STUDY POPULATION

9.1 Inclusion Criteria

1. Healthy female subjects aged 18 – 40 years.
2. Body mass index (BMI) ≥ 18 and ≤ 30 kg/m².
3. Subjects weight ≥ 50 kg and ≤ 100 kg at screening.
4. Able to voluntarily provide written informed consent to participate in the study.
5. Subjects are pre-menopausal.
6. Females of childbearing potential must have a negative pregnancy test at screening (β HCG) and prior to each dose. To prevent pregnancy female subjects of childbearing potential must take adequate contraceptive precautions for the entire duration of study participation (up to Day 85). Adequate and highly effective contraceptive precautions include:
 - Established use of oral, injected or implanted hormonal methods of contraception.
 - Placement of an intrauterine device (IUD) or intrauterine system (IUS).
 - Barrier methods of contraception: Condom or occlusive cap (diaphragm or cervical/vault caps) with spermicidal foam/gel/film/cream/suppository.
 - Male sterilisation (with the appropriate post-vasectomy documentation of the absence of sperm in the ejaculate). [For female subjects, the vasectomised male partner should be the sole partner for that subject].
 - True abstinence, when this is in line with the preferred and usual lifestyle of the subject. [Periodic abstinence (e.g., calendar, ovulation, symptothermal, post-ovulation methods) and withdrawal are not acceptable methods of contraception].
 - The chosen contraception method(s) must be followed from the first dose until at least Day 85 of the study.
7. Non-smokers for at least 3 months prior to first study vaccine administration.

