Based on the results from clinical use of other protein vaccines adsorbed to Alhydrogel®, and other aluminium containing adjuvants transient local reactions at the injection site, including pain, oedema, bruising, erythema and induration, mainly of mild intensity, are likely to occur. In addition, flu-like symptoms, such as fatigue, malaise, myalgia, and mild to moderate headache may occur.

The protocol requires that subjects are monitored after vaccine administration (vital signs and general signs and symptoms), with regular follow-up visits for physician assessment and questioning regarding AEs will be conducted for all subjects in the study. All study subjects will be monitored for potential side effects of vaccination during the entire course of the study, as per the protocol, and adverse events must be appropriately followed up.

GBS-NN/NN2 vaccination is contraindicated in subjects known to suffer hypersensitivity reactions to vaccines or a known allergy to aluminium hydroxide. For the purpose of the study subjects who have experienced a significant illness in the four weeks prior to check in will be excluded. The vaccine should not be given to subjects with known or suspected immune deficiency, autoimmune diseases or who have an acute infection.

GBS-NN/NN2 should not currently be given to women known, or suspected to be, pregnant, or to nursing mothers. Currently GBS-NN/NN2 should only be administered to women of child-bearing potential if adequate contraceptive precautions are taken, accompanied by serum and/or urine pregnancy testing prior to vaccination and during follow up.

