9.2 Exclusion Criteria

1. Subjects who have received GBS-NN vaccine previously.
2. Subjects with history or presence of significant cardiovascular disease, pulmonary, hepatic, gallbladder or biliary tract, renal, haematological, gastrointestinal, endocrine, immunologic, dermatological, neurological, psychiatric, autoimmune disease or current infection.
3. Pregnant or lactating females.
4. Laboratory values at screening which are deemed by the investigator to be clinically significantly abnormal.
5. Positive drug screen for drugs of abuse or a positive alcohol urine test prior to first dosing unless there is a documented medical explanation for the positive result other than drugs of abuse (e.g., the subject has been prescribed opioids for pain).
6. Positive for human immunodeficiency virus (HIV), hepatitis B or hepatitis C.
7. Participation in a clinical drug study during the 90 days preceding the initial dose in this study.

8. Any significant illness during the 4 weeks preceding check-in for this study (Day 1).
9. Subjects with a history of allergic reactions after previous vaccination.
10. Subjects who have received any vaccine within 30 days of screening, or who are planning to receive a vaccine up to Day 85 of the study.
11. Subjects receiving immunosuppressive therapy in the 6 months prior to screening, taking any short-term medications including over-the-counter (OTC) preparations, within 7 days of the first dose. Chronic medications such as antihypertensives, bronchodilators, oral contraceptives or statins that do not affect the immune system, will be permitted and allowed to continue during the study at the discretion of the Investigator. Paracetamol will be permitted for the treatment of headache or other symptoms. Use of OTC vitamins and dietary supplements is allowed
12. Subjects with tattoos at the proposed site of vaccine administration.
13. Donation of blood or blood products within 90 days prior to vaccine administration or intending to donate blood or blood products within 90 days of the last visit.
14. Subjects who, in the opinion of the Investigator, are unsuitable for participation in the study.

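### Criterion 6 sets no contraception lead-in before the first dose, so both pre-dose pregnancy tests could miss a very recent conception in some barrier users and possibly in women with a new IUD/IUS

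*Combined protocol and SAP*

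**What the plan says.** Section 9.1, criterion 6, requires a negative pregnancy test at screening and before each dose. It describes the contraception period twice. The opening sentence says that women of childbearing potential "must take adequate contraceptive precautions for the entire duration of study participation (up to Day 85"), and the closing item says "The chosen contraception method(s) must be followed from the first dose until at least Day 85 of the study". Only the second names a start.

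The permitted methods differ in what they imply about the time before Day 1. Hormonal contraception is worded as "Established use of oral, injected or implanted hormonal methods of contraception". Vasectomy needs documentation, and abstinence must be the woman's usual practice. The intrauterine option reads only "Placement of an intrauterine device (IUD) or intrauterine system (IUS"), and the barrier option has no condition on prior use.

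Section 8.3 sets study start at check-in on Day 1 and leaves the screening period out of the 12 weeks of involvement. Section 12.1 allows screening at any time in the 28 days before the first dose. Before dose 1 there are two pregnancy tests: serum at screening and urine on Day 1 (section 12.2 and the footnotes to the schedule in section 18). The next is a urine test at Visit 6, before dose 2.

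**The concern.** A pregnancy test cannot detect a conception that is more recent than its detection lag. A contraceptive lead-in normally covers that interval, and criterion 6 does not clearly require one. A woman who begins using condoms on Day 1, or whose device has just been placed, can meet every written criterion, test negative twice and already have conceived. She would then fall under exclusion 3, "Pregnant or lactating females", without anyone knowing.

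At stake is a first dose given in an undetected early pregnancy. Section 6.2.1 says that reproductive toxicology work was still being completed, and the trial is meant for non-pregnant women. The issue is subject protection. It does not bear on any estimate or test in the statistical section.

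**Working it through.** The plan states no figure on this point, so there is none to reproduce. The check asks how many days before Day 1 are covered neither by required contraception nor by a test.

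**Inputs from the documents.** Screening is d = 1 to 28 days before Day 1 (12.1, section 18). Visit 6 is 28 days after Visit 2, with a window of ±3 days in 12.2 and ±2 days in 12.4.

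**Assumptions, not in the documents.** Urine lag Lu and serum lag Ls are each 7 to 14 days. The interval f from intercourse to conception is 0 in the simple case and 1 to 5 days otherwise.

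**Formula.** Let s be the required days of contraception before Day 1. A conception is missed by the urine test if it lies less than Lu days before Day 1, and by the serum test if it lies less than d + Ls days before Day 1. Counted by date of unprotected intercourse, the uncovered days are:

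max(0, min(Lu, d + Ls) + f − s)

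| Requirement | f = 0 | f = 1 to 5 |
|---|---|---|
| From first dose (s = 0) | 7 to 14 | 8 to 19 |
| From screening on Day -1 (s = d = 1) | 6 to 13 | 7 to 18 |
| From screening on Day -7 (s = d = 7) | 0 to 7 | 1 to 12 |
| From screening on Day -14 (s = d = 14) | 0 | 0 to 5 |
| 14-day lead-in (s = 14) | 0 | 0 to 5 |
| 21-day lead-in (s = 21) | 0 | 0 |

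- **Whole days.** In the first row with f = 0, a 7-day lag misses conceptions 0 to 6 days before Day 1, and a 14-day lag misses those 0 to 13 days before.
- **Unequal lags.** The serum test helps only if it is the more sensitive and screening is late. With Ls = 7, Lu = 14 and s = 0, d = 1 gives min(14, 8) = 8 days, and d = 7 gives min(14, 14) = 14 days.
- **14-day lead-in.** With Lu = 14 and screening early enough that d + Ls is at least 14, the remainder is 14 + f − 14 = f, that is 1 to 5 days.
- **21-day lead-in.** The worst case is 14 + 5 − 21 = −2, so 0 days.

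**Exposure.** A conception 0 to 14 days before Day 1 is 28 to 42 days old at Visit 6. This becomes 25 to 45 days with the ±3-day window, or 26 to 44 with ±2. If conception follows Day 1 by up to 5 days, the minimum is 25 − 5 = 20 days. All of these exceed 14 days, so under the assumed lag the Visit 6 test would stop a second dose.

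**Placebo.** The synopsis assigns 6 of 30 in each cohort to placebo: 12 of 60, or one in five, with no antigen exposure.

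**The case against.** The best defence is that other provisions already do this work. Section 6.3 makes adequate contraceptive precautions a condition of giving the vaccine to women of childbearing potential, and also states "GBS-NN/NN2 should not currently be given to women known, or suspected to be, pregnant, or to nursing mothers". Section 10.3 allows randomisation only after every eligibility criterion has been verified. The schedule has an eligibility review at Visit 2, and exclusion 14 lets the investigator refuse "Subjects who, in the opinion of the Investigator, are unsuitable for participation in the study". An investigator checking criterion 6 would have to ask which method is used, and protocols seldom script such interviews. These safeguards are real and lower the risk. They remain partial: section 6.3 sets no start date, and a criterion without a lead-in can be fully verified in a woman who begins her method on Day 1. No listed assessment names the start date or recent unprotected intercourse.

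A second defence is that study participation can be read as starting at consent. That reading is possible, so a reader should not infer that the protocol unambiguously requires contraception only from Day 1. Section 8.3 points the other way, and so does the match between Day 85 and 12 weeks from Day 1 (84 days). Even the protective reading guarantees only one day.

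Third, nothing shows that women with a new device were unprotected beforehand, and placement may mean already in place. That group is therefore only possibly affected. The point about barrier users does not depend on it.

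**Conclusion.** The gap is real and minor. Under the assumed 7 to 14 day lag, a conception in the last 7 to 14 days before Day 1 could be missed by both pre-dose tests. The women concerned are barrier users without consistent prior use and possibly those with a newly placed IUD/IUS. Exposure would be at most one dose before Visit 6, and one subject in five receives placebo. Preliminary reproductive data show no adverse effect (6.2.1), pregnancies are followed up (14.7), and no endpoint or escalation rule is touched.

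Two stronger readings are tempting and unsupported. One is that such pregnancies are to be expected in this trial: the documents give neither the share of women using these methods nor a conception rate, so no expected number can be calculated. The other is that a 14-day lead-in would close the gap. It would do so only if conception fell on the day of intercourse and the method never failed. With a 14-day urine lag and an interval of 1 to 5 days, about that many days stay uncovered, and method failure during the lead-in remains possible at any length.

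**What to change.** In 9.1, criterion 6, require the chosen method from at least 14 days before the first dose (or the detection lag of the urine test actually used, if longer) until at least Day 85. Give the opening sentence the same start. Confirm and record method and start date at the existing Visit 2 eligibility review. Requiring contraception from screening would not be enough, since screening may be the day before dosing.

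If the sponsor also wants to cover the interval from intercourse to conception, 21 days covers 14 + 5 = 19 days. Counted from screening on Day -28, a 14-day lead-in leaves 28 − 14 = 14 days of slack and a 21-day lead-in leaves 28 − 21 = 7.

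No visit or test is added. Look-back periods are already familiar in the eligibility criteria, for example "Non-smokers for at least 3 months prior to first study vaccine administration". The cost is that some barrier users, or women with a new IUD/IUS, may be delayed or screened out. Women who can confirm earlier consistent use lose nothing.

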9.2 Exclusion Criteria

1. Subjects who have received GBS-NN vaccine previously.
2. Subjects with history or presence of significant cardiovascular disease, pulmonary, hepatic, gallbladder or biliary tract, renal, haematological, gastrointestinal, endocrine, immunologic, dermatological, neurological, psychiatric, autoimmune disease or current infection.
3. Pregnant or lactating females.
4. Laboratory values at screening which are deemed by the investigator to be clinically significantly abnormal.
5. Positive drug screen for drugs of abuse or a positive alcohol urine test prior to first dosing unless there is a documented medical explanation for the positive result other than drugs of abuse (e.g., the subject has been prescribed opioids for pain).
6. Positive for human immunodeficiency virus (HIV), hepatitis B or hepatitis C.
7. Participation in a clinical drug study during the 90 days preceding the initial dose in this study.

8. Any significant illness during the 4 weeks preceding check-in for this study (Day 1).
9. Subjects with a history of allergic reactions after previous vaccination.
10. Subjects who have received any vaccine within 30 days of screening, or who are planning to receive a vaccine up to Day 85 of the study.
11. Subjects receiving immunosuppressive therapy in the 6 months prior to screening, taking any short-term medications including over-the-counter (OTC) preparations, within 7 days of the first dose. Chronic medications such as antihypertensives, bronchodilators, oral contraceptives or statins that do not affect the immune system, will be permitted and allowed to continue during the study at the discretion of the Investigator. Paracetamol will be permitted for the treatment of headache or other symptoms. Use of OTC vitamins and dietary supplements is allowed
12. Subjects with tattoos at the proposed site of vaccine administration.
13. Donation of blood or blood products within 90 days prior to vaccine administration or intending to donate blood or blood products within 90 days of the last visit.
14. Subjects who, in the opinion of the Investigator, are unsuitable for participation in the study.

9.3 Planned Sample Size

60 healthy female subjects aged 18 to 40 will be randomised into 2 cohorts of 30 subjects.

At least 24 evaluable subjects in cohort 1 will be required to attend through to visit 4 in order to provide sufficient data for a decision to dose escalate in cohort 2. If the required number of evaluable subjects are not obtained in a cohort, then the safety review committee (SRC) must decide whether there is enough safety information available to make a decision or whether further subjects should replace the dropped subjects or if sufficient information exists to determine if the dosing of cohort 2 is appropriate.

9.4 Allocation of Randomisation Numbers

Subjects will be allocated to treatment groups according to a randomisation code produced by ████████ using the PROC PLAN procedure of SAS® version 9.3.

Subjects will be numbered sequentially from 001 (i.e. 001, 002 etc.). Replacement subjects will be assigned the same randomisation as the subject they are replacing, however, 100 will be added to the number (i.e. 101 would replace 001 etc.).

9.5 Subject Withdrawal

The subject has the right to abstain from participation in the study or to withdraw consent to participate at any time. The Sponsor or the Investigator also holds the responsibility to withdraw a randomised subject from the study prematurely if it is considered in the best interest of the subject. The entire study may be stopped if there are unpredicted safety concerns.

A subject's participation may be discontinued at any point during the study without implications on further medical care if:

- They no longer wish to participate.
- The physician feels it is in their best interest to withdraw.
- The subject deviates from the treatment plan specified in the protocol (e.g. failure to attend essential or significant amount of study visits).

- The subject is no longer willing to comply with the requirements of the study protocol.
- The study is prematurely terminated, see Section 9.7.

If the participation of any subject ceases prematurely, the reasons leading to withdrawal from the study should be described in detail. A post-study medical should be performed as described in Section 12.2. The case report form (CRF) must be completed as fully as possible giving reasons for withdrawal when available. If a subject become pregnant between Day 1 (first dose) and Day 85, she will not receive any further vaccinations (if conception occurs between the first and second dose) but will undergo all follow-up visits and the pregnancy will be followed to term to determine the outcome unless the subject withdraws consent.

9.6 Subject Replacement

If the required number of evaluable subjects are not obtained in a cohort, then replacement subjects may be recruited as per section 9.3.

9.7 Premature Termination of the Study

Following review by the Sponsor and the Investigator, the study may be terminated prematurely if:

- There are new toxicological or pharmacological findings, serious adverse events (AEs) or frequent severe AEs likely to be related to the vaccine that invalidate the positive benefit-risk assessment.
- AEs occur in such prominence (i.e. severity and frequency) that the proposed schedule can no longer be adhered to.
- Significant protocol deviations occur at a frequency implicating the valid and safe conduct of the study.
- The Sponsor decides to discontinue the study.

The individual stopping criteria and study stopping criteria are described in Sections 12.6 and 12.7.

10. INVESTIGATIONAL MEDICINAL PRODUCT

10.1 Identity and Doses of IMP

The GBS-NN/NN2 vaccine will be supplied [REDACTED]

Individual subject treatments will be dispensed by the pharmacist or designee and labelled in accordance with Annex 13 of “The Rules Governing Medical Products in European Community, volume 4 Good Manufacturing Practice for Medicinal Products”. Finished doses will be certified by the [REDACTED] Qualified Person.

The following dosing strategy will be employed:

Cohort	Dose schedule	Dose level GBS-NN/NN2 or placebo
1	Day 1, 29	25µg of each protein or placebo
2	Day 1, 29	50µg of each protein or placebo

10.2 Rationale for doses

[REDACTED] Hence, investigating the immune response of doses of 25 µg and 50 µg of each fusion protein was determined to be the most appropriate doses. There are no data to suggest that different amounts of each fusion protein are required and therefore equal amounts of each is considered appropriate.

10.3 Randomisation

Subjects will be randomised pre-dose on the morning of Day 1, once all eligibility criteria have been verified. A randomisation list will be held on site, which will be accessible only to unblinded study personnel.

10.4 IMP Administration

Administration will be by intramuscular injection into the deltoid muscle of one of the subject's arms. For the second dose the subjects opposite arm should be used in the event that the first injection site has not healed.

10.5 Blinding

This is a double-blind study. The study vaccine will be prepared at the study site by an unblinded pharmacy team as detailed in a separate pharmacy instruction manual. The Investigator will have access to emergency envelopes at all times. In case of an emergency or any finding that requires unblinding to determine the identification of the treatment

administered for the appropriate management of a subject on the study, the Investigator may break the blinding code for an individual subject. If the blind is broken the Investigator will inform the Sponsor within 24 hours of breaking the blind, that the blind has been broken and the reason for breaking the blind (but not necessarily the outcome of the breaking of the blind) and record the date/time and reason for breaking the blind.

10.6 Vaccine Accountability and Storage

The Investigator and study staff will be responsible for the accountability of all study vaccines (dispensing, inventory and record keeping) and adherence to Good Clinical Practice (GCP) guidelines as well as appropriate regulations. Study vaccines will be stored according to the instructions on the label as received by the manufacturer. Storage of GBS-NN and GBS-NN2 will be ██████████ Alhydrogel® and diluents buffer will be stored at 2 to 8°C.

The Investigator will not allow the study vaccine to be used other than as directed by this protocol. Study vaccines will not be dispensed to any individual who is not randomised in the study.

An accurate and timely record of the receipt of all study vaccines, dispensing to subjects, collection of unused study vaccines returned, and subsequent return of unused study vaccines to the Sponsor (or designated distributor) must be maintained. This includes, but may not be limited to, receipt of study vaccines, IMP accountability logs, IMP return documentation and shipping receipts.

The supplies and inventory records must be made available, upon request, for inspection by the designated representative of the Sponsor or a representative of a regulatory authority. All unused study vaccines will be reconciled and handled in agreement with the Sponsor.

The Investigator must ensure the availability of an appropriate storage location and the recording and evaluation of storage conditions. The Pharmacy Department will keep an inventory. This will include a description of the formulation and the quantity of investigational materials received for the study and a record of the materials that are dispensed, to whom and when.

Upon termination of the study the pharmacist or designee will conduct a final inventory of the medication supply and will record the results of this inventory in the Drug Accountability Form. Unused medication will be returned to the Sponsor (or designated distributor) or destroyed at the end of the study according to instructions provided by the Sponsor.

